## 12.1 Recording of Reportable Events

At each tele-visit the study team member will assess REs by recording all voluntary complaints of the participant and by assessment of clinical features.

All REs, whether observed by the Investigator or volunteered by the participant, should be recorded on the eCRF RE Log. This will include the type and description of the event, the date of onset, investigator opinion of relatedness to study participation, and any action taken. This recording will commence with the institution of protocol-specific procedures and continue until either withdrawal or study completion.

The CHeT Site Investigator will comply with the UR Institutional Review Board (IRB) regulations regarding the reporting of reportable events.

## 12.2 Emergency Actions

A Medical Safety Escalation Plan has been created for urgent and non-urgent medical situations (see Operations Manual). The purpose of the Medical Safety Escalation Plan is to responsibly manage complex or acutely escalating medical issues that may arise during a tele-visit to ensure participant safety.

## 13. STATISTICAL ANALYSIS

Planned analyses are summarized here. Additional details will be included in a separate Statistical Analysis Plan (SAP). In the event of a conflict between the protocol and the SAP, the SAP will take precedence.

### 13.1 Data Processing and Quality Control (QC) for Smartphone (SP) Based Measures:

Data QC and cleaning: As data from the SP are deposited on a daily basis into Synapse, we will have a clear measure of compliance and engagement. Additionally, data streams can be monitored for quality. Data scientists and statisticians at Sage Bionetworks have developed an extensive pipeline to monitor and QC active task measurements from smartphone applications (e.g., <https://github.com/Sage-Bionetworks/mpowertools>). These tools will be adopted and expanded to monitor and QC passive data streams. During the development stage of the application we will run small scale internal experiments where user use Android and iOS devices concurrently to establish bounds on differences between devices.

Data processing/feature extraction: Quality processed data will be summarized into features using extensions of our feature extraction pipelines for active tasks. These include but are not limited to time and frequency domain statistics, energy and entropy of frequency spectrum from the tri-axial accelerometer, along with absolute displacement measurements. For displacement information (Aim 3b) data will be summarized into variables such as furthest distance traveled, frequency of trips, average daily distance etc. Also, additional specific features will be selected based on previously published

studies using passive data and expert knowledge of behavioral patterns of PD patients. These measures will be summarized to a single measure by training a n-fold cross-validated machine learning model using the discovery data subset. Additionally, features will be evaluated by test-retest reliability across time. Data analysis will be performed as described in SA 3.B and 3.C below.

## 13.2 Statistical Analysis Plan

**Aim 1:** To evaluate concordance between in-clinic and tele-visit MDS-UPDRS assessments (Aim 1b), we will use results from the REACT-PD study to calibrate tele-visit assessments to in-clinic MDS-UPDRS scores, matching means and standard deviations cross-sectionally. We will use Lin's concordance correlation coefficient,  $r_c$ , to summarize accuracy of the calibrated tele-visit estimates vs. scores collected from in-person SURE-PD3 and SUPER-PD visits conducted close in time, accepting tele-visit estimates as sufficiently accurate if  $r_c > 0.8$ . If we observe insufficient concordance, we will investigate contributions of bias, scale difference, and imprecision and re-calibrate using all available data from both REACT-PD and the current study.

**Aim 2:** We will assess the calibration and correlation between tele-visit (TV) and SP metrics both cross-sectionally and longitudinally (Aim 2a). We will generate SP-derived metrics that best match composite scores of motor function (MDS-UPDRS part 3), non-motor function (MoCA total score), subjective function (including global impression (CGI) scores, Schwab and England ADL scores, MDS-UPDRS parts 1b and 2 scores, and estimates of MDS-UPDRS part 1-3 total scores. We will randomly split our sample 2:1 into calibration and validation subsets. For each measure, we will use the calibration sample to develop a transformation of SP data that best matches the TV measurement machine learning models using a variety of machine learning techniques with a final selection based on overall accuracy by 10-fold cross-validation. We will test the accuracy of calibrated SP measures in the reserved validation sample using Lin's concordance correlation coefficient,  $r_c$ . If we observe insufficient concordance, we will investigate contributions of bias, scale difference, and imprecision and re-calibrate using all available data from both the calibration and validation samples.

We will compare TV vs. calibrated SP measures of disease progression generally, as predictors of future clinical events and changes in patient reported outcomes, and between specific subsets of participants expected to progress at different rates (Aim 2b) due to biology or treatment. After calibration, we will estimate the standard error for a treatment-group comparison from a two-arm trial using measure-specific variance components from a bivariate random-slopes linear mixed model for each pair of TV and SP measures and assuming an assessment schedule appropriate for each measure, e.g., annual for TV measures and quarterly for SP measures. Preferred measures would have smaller standard errors, and specifically, the ratio of squared standard errors provides an estimate of the relative sample size required. We will use the same approach to identify measures that are significantly more sensitive to biological

subgroups (e.g., among participants stratified by their rate of MDS-UPDRS progression over the first 2 years of in-clinic follow-up in the parent trials) or treatment-based subgroups (e.g., participants randomized to Isradipine or serum urate elevation). To compare TV assessments and SP measures with respect to their accuracy in predicting future clinical events and changes in patient reported outcomes, we will use the same 2:1 training: validation split and train separate models using TV and SP metrics collected over the first year of follow-up to predict clinical events and changes in PROs over the second year of follow-up. Clinical events will include dropping below 80% on the modified Schwab and England ADL and experiencing a fall. PROs of interest will include summary scores from the PDQ-8, EQ-5D, and PDAQ-15 and measures derived from the PD-PROP. Selection of the best training models will be based on 10-fold cross-validated accuracy for binary outcomes and residual sum of squares for continuous measures. Positive and negative predictive values of TV and SP-derived predictions will be estimated from the validation sample for binary outcomes and compared by logistic regression. For continuous outcomes, RSS estimates will be compared between TV and SP-derived predictions. As an exploratory analysis, additional models that combine TV and SP measures will be constructed and tested for accuracy relative to models derived from TV or SP measures alone.

Completion rates of PROs collected during TVs vs. those collected online via FI will be compared by mixed effect logistic regression with participant-specific and participant x form random effects (Aim 2c). Concordance between PROs assessed during TVs vs. those obtained online via FI will be estimated using Lin's concordance correlation coefficient (Aim 2c).

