
Statistical Analysis (by Specific Aim)
	
SA 1: We will use results from the REACT-PD study to establish a calibration of tele-visit (TV) assessments to predict in-clinic MDS-UPDRS scores (Aim 1b). Lin's concordance correlation coefficient, <math>r_c</math>, will be used to summarize accuracy of the calibrated TV estimates vs. scores collected from in-person SURE-PD3 visits conducted close in time, accepting TV estimates as sufficiently accurate if <math>r_c > 0.8</math>. If we observe insufficient concordance, we will recalibrate using all available data from both REACT-PD and the current study.
 
SA 2: The study sample will be randomly split 2:1 into calibration and validation subsets. The calibration sample will be used to derive smartphone (SP) measures that best match the TV assessed composite scores of motor function (MDS-UPDRS part 3), non-motor function (MoCA total score), subjective function (including clinical global impression [CGI] scores, patient global impression scores, modified Schwab and England ADL scores, and MDS-UPDRS parts 1b and 2 scores), and estimates of MDS-UPDRS part 1-3 total scores (Aim 2a). The accuracy of calibrated SP measures will be tested in the reserved validation sample using Lin's concordance correlation coefficient, <math>r_c</math>. If we observe insufficient concordance, we will recalibrate using all available data from both the calibration and validation samples.
 
TV assessments and calibrated SP measures of disease progression will be compared generally and between specific subsets of participants expected to progress at different rates (Aim 2b). Each measure will be standardized to 30% of the observed mean change over 2 years based on a random-slopes linear mixed model of the full sample such that a one-unit change of all standardized, calibrated measures would reflect an equivalent magnitude of change relative to natural rates of progression. Estimated measure-specific variance components will be used to estimate the standard error for a treatment group comparison from a two-arm trial assuming an assessment schedule appropriate for a given measure, e.g., annual for TV measures and quarterly for SP measures. The ratio of squared standard errors will be used to estimate the relative sample size required using one or another measure for designs with equivalent power. The same approach will be used to identify measures that are sensitive to biological subgroups (e.g., among participants stratified by their rate of MDS-UPDRS progression over the first 2 years of in-clinic follow-up in the parent trials) or treatment-based subgroups (e.g., participants randomized to isradipine or serum urate elevation). TV assessments and SP measures will also be compared with respect to their accuracy in predicting future clinical events and changes in

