
Power Calculations
	
SA 1b. With a sample size of ~10 SURE-PD3 participants expected to complete at least one TV close in time to their in-person clinic visit, the study will have 80% power to conclude that the REACT-PD calibrated tele-visit estimates are sufficiently accurate (<math>r_c > 0.8</math> at <math>\alpha = 0.05</math>) if the true concordance is at least 0.89.
 
SA 2a. With a 2:1 split of ~340 AT-HOME PD participants, yielding ~115 participants contributing to validation tests, the study will have 80% power to declare a given SP measure sufficiently accurate (<math>r_c > 0.80</math> at <math>\alpha = 0.05</math>) if the true concordance is at least 0.87.
 
SA 2b. With approximately 80% of participants participating in the SP portion of the study, yielding ~340 participants contributing to the smartphone vs tele-visit comparison, the study would have an 80% probability of selecting the true preferred measure from a pair of TV or SP if the preferred measure had lower standard error by an effect size of at least 0.065.
 
SA 3. With a 2:1 split of ~240 participants, yielding ~80 in the validation sample and at least 25% experiencing at least an 8-point progression in MDS-UPDRS parts 1-3 total score, the study would have 80% power to declare a novel measure derived from passive SP monitoring to have a ROC AUC significantly greater than 0.80 if the true AUC were at least 0.95.

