Data Management	
Data collected during tele-visits will be entered and maintained in REDCap (a secure web-based survey and data management system). Each participant’s baseline demographic information, concomitant medications, and health history as well as clinical data including PD-PROP from the corresponding SUPER-PD visit, will be transferred from the SUPER-PD REDCap project to the AHPD sub-study REDCap project. All data will ultimately be transferred to Synapse (an open source collaborative platform) for analysis. For any sub-study participants who are participating in the mPower 2.0 component of SUPER-PD, their smartphone data from the corresponding SUPER-PD visit and associated remote 2-week burst will be linked with AT-HOME PD data within Synapse.
 
From Synapse, the cleaned, processed, and event date- and time-transformed dataset will be transferred to the PDBP’s Data Management Resource for further distribution to PDBP investigators and will be made available to the wider research community through their qualified researchers program.

Statistical Analysis	Paired MDS-UPDRS and MoCA scores from in-person and TV assessments of SUPER-PD participants will be pooled with data from SURE-PD3. The accuracy of predicted in-clinic scores based

	
on TV assessments using calibrations from REACT-PD will be summarized by Lin's concordance correlation coefficient, <math>r_c</math>, equivalent to an intra-class correlation (ICC). The REACT-PD calibrations will be judged sufficiently accurate if <math>r_c > 0.8</math>. If we observe insufficient concordance, we will re-calibrate using all available data from REACT-PD, SURE-PD3, and SUPER-PD.

Sample Size	
With a combined sample size of ~60 SURE-PD3 and SUPER-PD participants expected to complete at least one TV close in time to their in-person clinic visit, the study will have 80% power to conclude that the REACT-PD calibrated tele-visit estimates are sufficiently accurate (<math>r_c > 0.8</math> at alpha = 0.05) if the true concordance is at least 0.89.

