**2) Reliability:**

*There was excellent correlation between in-person visits and tele-visits for non-motor outcome measures. Intra-class correlation (ICC) coefficients for the Montreal Cognitive Assessment (MoCA), MDS-UPDRS 1A, MDS-UPDRS 1B, and MDS-UPDRS II were 0.78, 0.83, 0.88, and 0.90 respectively. There was good correlation for the MDS-UPDRS Part III (ICC 0.53).*

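### Aim 1b accepts tele-visit scores when r_c exceeds 0.8, but the stated alpha of 0.05 and 80% power belong to a one-sided test the rule does not contain, and cannot hold at the main synopsis's n of about 10

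*Combined protocol and SAP*

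**What the plan says.** **The decision rule** appears in three places, each time without a confidence limit, a test or sidedness:

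- Section 13.2, Aim 1: "accepting tele-visit estimates as sufficiently accurate if" r_c is above 0.8. The consequence of failing is: "If we observe insufficient concordance, we will investigate contributions of bias, scale difference, and imprecision and re-calibrate using all available data from both REACT-PD" (pooled with this study's own pairs).
- Main synopsis, Statistical Analysis, SA 1: the comparison is with "scores collected from in-person SURE-PD3 visits conducted close in time, accepting TV estimates as sufficiently accurate if" r_c is above 0.8. SUPER-PD is not mentioned here, although section 13.2 includes it.
- SUPER-PD sub-study synopsis, Statistical Analysis: "The REACT-PD calibrations will be judged sufficiently accurate if" r_c is above 0.8, and otherwise "If we observe insufficient concordance, we will re-calibrate using all available data from REACT-PD, SURE-PD3, and SUPER-PD".

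**The sample-size text** gives the same conclusion 80% power at a true concordance of 0.89, with r_c > 0.8 at alpha = 0.05 in parentheses:

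- Section 13.4, SA 1b: about 10 SURE-PD3 plus about 50 SUPER-PD participants.
- Sub-study synopsis, Sample Size: "With a combined sample size of ~60 SURE-PD3 and SUPER-PD participants".
- Main synopsis, SA 1b under Power Calculations: "With a sample size of ~10 SURE-PD3 participants expected to complete at least one TV close in time to their in-person clinic visit", with power, alpha and 0.89 unchanged.

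The opening of section 13 leaves further detail to a separate SAP, which is not among the documents and takes precedence in a conflict.

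**The concern.** A rule that compares an estimate with 0.8 and a 5% test that the true value exceeds 0.8 are different rules. The plan writes the first and quotes error rates that belong to the second. An observed r_c between 0.80 and about 0.866 would pass under section 13.2 and fail the test implied by section 13.4. It would then be reported as sufficiently accurate, without the planned look at bias, scale difference and imprecision and without recalibration, yet the conclusion would not carry the 5% error rate attached to it.

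Separately, one power statement is made for both about 60 and about 10 participants. It cannot be true of both.

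**Working it through.** **Inputs.** Threshold 0.80, true value 0.89, alpha 0.05, power 80%, n = 60 (section 13.4 and sub-study synopsis) or n = 10 (main synopsis). The sub-study synopsis treats r_c as equivalent to an ICC, so Fisher's z is a reasonable scale. Scores are assumed bivariate normal with no location or scale bias left after calibration.

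**Formula.** Power = Φ[(atanh 0.89 − atanh 0.80) × √(n − k) − z_crit], with k = 3 or 2. Here z_crit is 1.645 (one-sided 5%), 1.960 (two-sided 5%) or 0 (rule on the estimate alone). atanh 0.89 = 1.4219 and atanh 0.80 = 1.0986, a difference of 0.3233.

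**The plan's figure at n = 60 (k = 3).** 0.3233 × √57 = 2.441.

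- One-sided: Φ(2.441 − 1.645) = 78.7% (79.3% with k = 2). This matches the stated 80%.
- Two-sided: Φ(2.441 − 1.960) = 68.5% (69.2% with k = 2). This does not.
- Estimate alone: Φ(2.441) = 99.3%.

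The observed value needed for the one-sided test is tanh(1.0986 + 1.645/√57) = 0.866. For 80% power, n = [(1.645 + 0.842)/0.3233]² + 3, about 62 one-sided. With 1.960 in place of 1.645 it is about 78. The planned 60 therefore fits a one-sided calculation. SA 2a shows the same pattern (n = 115, true 0.87): 79-80% one-sided, 69-70% two-sided.

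**n = 10.** 0.3233 × √7 = 0.855. One-sided power is Φ(0.855 − 1.645) = 21.5% (23.3% with k = 2). The estimate-alone rule gives Φ(0.855) = 80.4% (82.0% with k = 2).

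**Acceptance probabilities.** Ranges span Fisher's z and simulation of Lin's r_c (200,000 runs per cell, lower limit from Lin's variance on the z scale).

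| n | True r_c | Estimate > 0.80 | One-sided 95% lower limit > 0.80 |
|---|---|---|---|
| 60 | 0.53 | under 0.01% | 0% |
| 60 | 0.78 | 32-34% | 2% |
| 60 | 0.80 | 48-50% | 4.5-5% |
| 60 | 0.85 | 87-88% | 31-33% |
| 60 | 0.89 | 99% | 78-79% |
| 10 | 0.80 | 44-50% | 4-5% |
| 10 | 0.89 | 79-82% | 21-23% |

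At n = 10 the estimate-alone rule gives the stated power but not the alpha, and the test gives the alpha but not the power. The test reaches 80% only at a true r_c of about 0.96-0.97.

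**Which measures are exposed.** The sub-study collects only MDS-UPDRS part 3 and MoCA (its synopsis and Table 3), so n of about 60 applies to those two. Section 1.2 reports REACT-PD ICCs of 0.53 for part 3 and 0.78 for MoCA. If those values carried over after calibration (an assumption), both rules would almost never accept part 3. MoCA, below the threshold, would be accepted 32-34% of the time under the written rule and 2% under the test.

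**The case against.** The best defence is that the test is already there. The sample-size text ties r_c > 0.8 to alpha = 0.05 for the very conclusion the decision rule names; the claim is directional, so one-sided is the natural reading; and the separate SAP may state the confidence limit. This is probably what was intended. But the parenthesis stands only in the power text. No decision rule repeats it, sidedness is not given, and nothing says that failing the test leads to recalibration. The unseen SAP may supply the limit, but as written the protocol's rule and its power statement disagree.

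A second point is that the consequences are small. That is largely right. Failing leads only to investigation and recalibration, and nothing in Aims 2 or 3 is made conditional on the result. Aim 1 in section 13.2 and the main synopsis speak of MDS-UPDRS; MoCA comes under the rule only through the sub-study synopsis. About 50% acceptance at the boundary is also what any rule on an estimate gives, and for a mere recalibration trigger such a rule is defensible. It cannot then be described as having alpha = 0.05 at 0.80.

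Third, excluding a two-sided test depends on there being no residual bias. In simulation at n = 60 and true r_c 0.89, a two-sided limit based on Lin's variance has about 70% power with a residual mean shift of 0.2 SD and about 82% with 0.4 SD. So sidedness cannot be inferred with certainty, which is a reason to state it. The literal rule still accepts 47-48% at true 0.80 with either shift.

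Finally, the figure of about 10 is probably left over from an incomplete update. That explains the error but does not correct it.

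**Conclusion.** The concern holds. At n of about 60 the written rule accepts 48-50% at a true r_c of 0.80, against the stated 5%. The stated alpha and power correspond to a one-sided lower-limit rule with a cut-off near 0.866. At the main synopsis's n of about 10, neither rule gives both stated figures, so that power statement is wrong on either reading.

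These numbers rest on bivariate normality and no residual location or scale bias. The MoCA illustration also assumes that the REACT-PD value carries over. The matter should be corrected; its reach is limited to the recalibration decision and the reported accuracy of tele-visit scores.

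**What to change.** Preferred change:

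- In section 13.2 (Aim 1) and both synopses, accept if the one-sided 95% lower confidence limit for r_c exceeds 0.80; otherwise the planned investigation and recalibration follow.
- State that alpha = 0.05 is one-sided in section 13.4 and both synopses, including SA 2a.
- In the main synopsis, replace about 10 SURE-PD3 participants with the combined figure of about 60, and add SUPER-PD to the SA 1 comparison so that it agrees with section 13.2.
- State that n of about 60 applies to MDS-UPDRS part 3 and MoCA.

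Alternative: if r_c > 0.8 is meant only to trigger recalibration, keep it. Then remove the SA 1b alpha and power claim, or replace it with the rule's actual behaviour at n of about 60: about 5% acceptance at true 0.71, 48-50% at 0.80, 80% at 0.84 and 99% at 0.89. The main synopsis still needs aligning.

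Either way the cost is a clause in each place and one corrected sample size, with no new data. The lower-limit rule has a price: at a true r_c of 0.85, acceptance falls from 87-88% to 31-33%, so scores that truly exceed 0.80 would often be recalibrated. The alternative avoids that but gives up the 5% error claim.

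### Smartphone measures that fail Aim 2a are re-calibrated on the validation participants as well, and nothing keeps those scores out of the Aim 2b event prediction that relies on the same hold-out

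*Combined protocol and SAP*

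**What the plan says.** Section 13.2, Aim 2, splits the sample 2:1 at random. In the larger part, for each measure, the plan will "develop a transformation of SP data that best matches the TV measurement machine learning models using a variety of machine learning techniques", with the final model chosen by 10-fold cross-validation. The result is tested in the reserved third by Lin's concordance coefficient, r_c. The TV targets include "subjective function (including global impression (CGI) scores, Schwab and England ADL scores". If concordance is insufficient, "we will investigate contributions of bias, scale difference, and imprecision and re-calibrate using all available data from both the calibration and validation samples". The synopsis (Statistical Analysis, SA 2) has the same fallback: "If we observe insufficient concordance, we will recalibrate using all available data from both the calibration and validation samples".

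Aim 2b in the same section opens: "We will compare TV vs. calibrated SP measures of disease progression generally, as predictors of future clinical events and changes in patient reported outcomes". For the prediction part, "we will use the same 2:1 training: validation split and train separate models using TV and SP metrics collected over the first year", with events and PRO changes in the second year as outcomes. "Clinical events will include dropping below 80% on the modified Schwab and England ADL", and also a fall. "Positive and negative predictive values of TV and SP-derived predictions will be estimated from the validation sample" for binary outcomes.

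Section 13 leaves further detail to a separate SAP that takes precedence. That SAP is not among the supplied documents.

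**The concern.** Schwab and England is both a target of the Aim 2a mapping and the source of a named Aim 2b event. If a failed mapping is refitted on all participants, the validation participants' own Schwab and England scores help to build the SP score. That score is then judged on whether the same people fall below 80%. The route is more direct if month 24 is in the refit, because the month-24 score can define the year-2 event. The text neither includes nor excludes that visit.

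The effect would be one-sided. TV scores enter as observed and are not refitted to validation participants, so only the SP figure would be optimistic in a head-to-head comparison that is a stated objective (Section 2.1, Aim 2b). It would also be largest for the SP measures that had failed by most.

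**Working it through.** **1. What the text fixes and what it leaves open.** Failure leads to re-calibration on both subsets; that is stated. Two links are not.
- *Refit or correction?* For a refit: Aim 2 calibration is itself machine learning, and imprecision is listed among the causes to investigate. A linear correction cannot raise correlation, so it cannot cure imprecision. Against: almost the same fallback sentence appears under Aim 1, where calibration means matching means and standard deviations.
- *Which SP inputs?* The opening sentence of Aim 2b says calibrated measures. The operational sentence says only SP metrics. The synopsis uses the word calibrated for the progression comparison and drops it for event prediction.

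**2. The plan's own figure, and how often the fallback could apply.** Section 13.4 (SA 2a) gives n of about 115, threshold 0.80, true r_c 0.87, alpha 0.05 and power 80%. By Fisher's z, power = Φ[(atanh 0.87 − atanh 0.80)·√(n − 3) − z]. With one-sided z = 1.645, (1.3331 − 1.0986)·√112 − 1.645 = 0.836, so power is 79.9%. The figure reproduces; two-sided it would be 69.9%. If insufficient means failing that test, one measure triggers the fallback with probability 20% at true r_c 0.87, 49% at 0.85 and 95% at 0.80. If it means a point estimate of 0.80 or less, the probabilities are about 1%, 5% and 50%.

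**3. Bias or scale correction.** Replacing a score x by a + bx with b > 0 changes no ranking. Validation PPV, NPV and AUC are unchanged (simulated difference 0.000).

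**4. Full refit, main simulation (all settings below are assumptions).** 340 people, split 227/113; visits at 0, 12 and 24 months. Schwab and England = level (mean 92, SD 7) + slope (−3 per year, SD 3) + noise (SD 4), rounded to tens. Event: at least 80 at baseline and month 12, below 80 at month 24; rate about 10%, or about 11 validation events. 200 features, because Section 15.5 speaks of hundreds of measures; one fifth carry signal in the settings with signal. Ridge mapping; then a logistic event model on the baseline and month-12 scores, fitted in the training subset only. R, the share of non-signal feature variance that is stable between visits, is 0.8. 150 replicates. Arrows run from split intact to after a refit that includes month 24.

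| First r_c | PPV | NPV | AUC | AUC, refit to month 12 only |
|---|---|---|---|---|
| about 0 | 0.10 → 0.30 | 0.90 → 0.92 | 0.49 → 0.75 | 0.67 |
| about 0.37 | 0.24 → 0.38 | 0.92 → 0.93–0.94 | 0.70 → 0.84 | 0.80 |
| about 0.66 | 0.40 → 0.51 | up about 0.01 | 0.85 → 0.91 | 0.88 |
| about 0.78 | 0.56 → 0.60 | 0.949 → 0.953 | 0.92 → 0.94 | not available |

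Over R from 0.3 to 1.0 the PPV rise is 0.15–0.22, 0.08–0.20 and 0.06–0.14 in the first three rows. The single-study SD of PPV is 0.09–0.18.

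**5. How much depends on month 24.**
- Same features, R and event rate, 40 replicates. No signal: PPV 0.12 → 0.22 without month 24 and 0.33 with it, a ratio of rises of 0.10/0.21 = 0.48. First r_c about 0.58: 0.34 → 0.37 and 0.42, ratio 0.03/0.08 = 0.38.
- A differently built simulation, 20% event rate, 100 runs. No signal: 0.193 → 0.393 without and 0.185 → 0.462 with month 24, ratio 0.200/0.277 = 0.72. With signal, against an equal-size fit that excludes validation participants: 0.518 versus 0.464 and 0.565 versus 0.474, ratio 0.054/0.091 = 0.59. The equal-size comparison shows that the gain is optimism, not the benefit of more data.

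**6. Few features.** With 20 informative features, the second simulation gives PPV 0.479 versus 0.462 and 0.510 versus 0.490, an optimism of about 0.02. With 10 features in the main simulation, the AUC shift is 0.02–0.06 at r_c about 0, about 0.01 at 0.40 and below 0.01 at 0.69 or more.

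**The case against.** The plan already states the protective rule: the same split, with predictive values from the validation sample. It never directs that scores trained on validation participants be used there. The leak appears only when two steps are chained, and each link has a harmless reading. That stands, and it is why the point is conditional.

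The size is also open to challenge. Event rate, feature structure and R are assumed. The hundreds of measures describe the whole sensor pipeline, not the inputs to one Schwab and England model. AUC is not a planned Aim 2b metric, NPV hardly moves, and the largest PPV shifts need both an SP measure without signal and month 24 in the refit. All of this stands.

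Four stronger readings are tempting, and the documents do not support them:
- *Aim 2b is invalid as planned.* A bias or scale correction, or raw features modelled in the training subset, would leave it sound.
- *All Aim 2b outcomes are affected.* Falls and the named PROs are not Aim 2a targets, so the claim is limited to the Schwab and England event.
- *A post-refit r_c is passed off as validated.* The plan makes no such claim. Keeping the first r_c as the result is good practice, not the correction of an error.
- *SP measures can be expected to fail.* The REACT-PD coefficients of 0.53 to 0.90 (Section 1.2) compare tele-visit with in-person scores, and Section 1.1 reports R = 0.89 for smartphone tapping against the in-clinic motor exam. Neither predicts r_c for the measures calibrated here.

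**Conclusion.** The concern holds conditionally. A stated fallback can undo the hold-out on which the Aim 2b predictive values rest, and no supplied text prevents it. Three things must coincide: the measure fails Aim 2a, re-calibration is a refit of the mapping, and calibrated scores enter the event models. The last two are undecided in the text, and the separate SAP may settle them.

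The documents give no basis for a size. Under the assumptions above with 200 features, optimism in SP PPV is large, about 0.1 to 0.2, when SP carries little or no signal. Leaving month 24 out of the refit cuts the PPV rise to about half or less at a 10% event rate, and to about 60–70% at a 20% event rate. For a measure that narrowly fails, or with few features, it is a few hundredths and within single-study noise. I rate this a cheap improvement of minor to moderate severity.

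**What to change.** In Section 13.2:
1. State whether re-calibration is a bias/scale correction or a refit, and whether the Aim 2b event models take calibrated SP scores or raw features. If either harmless reading is meant, one sentence closes the point.
2. For Aim 2b event prediction in validation participants, use SP scores from the calibration-subset fit only. If a measure is refitted, use cross-fitted scores with whole participants as folds, so that nobody is scored by a model trained on their own data.
3. Treat any all-data re-calibration as a final model, and keep the first validation-sample r_c as the Aim 2a result.

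In simulation both routes in (2) return the no-signal AUC to 0.49–0.51 in the main settings (0.53 for cross-fitting with about 6 events). The cost is wording, a little computation and slightly noisier scores: r_c in 2,000 simulated new people was 0.36 for the calibration-only fit versus 0.38 for the all-data fit, 0.66 versus 0.67, and 0.79 versus 0.79.
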